9.3 Variables

The following variables will be collected for this study (pending availability):

Several biometric parameters will be measured in a time-dependent manner using the Vivalink wearable device. Values measured from day 8 to 14 will be used as baseline data (e.g. for determining parameter changes during the observation period or as co-factor in model building) unless this time period is within a 2-week distance of an exacerbation. In this case the next 7-day period with a distance of 4 weeks from an exacerbation will be considered the baseline in this context.

Variables measured with the Vivalink wearable device (including, but not limited to):

- Physical activity including stair climbing, (calculated based on continuous accelerometer measurement) [daily average] (derived parameter)
- Heart rate as beats per minute [daily average] (derived parameter)
- Resting heart rate (resting state as determined by accelerometer, beats per minute) [daily average] (derived parameter)
- Heart rate variability reflecting differences in time intervals between 2 R-waves in the ECG (milliseconds) [daily average (where applicable) of the following parameters: SDRR (standard deviation of RR intervals), SDNN (standard deviation of NN intervals), SDNNI (Mean of the standard deviations of all the NN intervals for each 5 min segment of a 24 h HRV recording), RMSSD (Root Mean Sum of Squared Distance), ln(RMSSD) (natural logarithm of RMSSD), pNN50 (percentage of successive RR intervals that differ by more than 50 ms) SI (stress index), LF power (low frequency fraction of HRV, 0.04 – 0.15 Hz), HF power (high frequency portion of HRV, 0.15 – 0.40 Hz), LF/HF (ratio of LF-to-HF power); for details of calculation check see [Shaffer 2017](#)] (derived parameters).
- Temperature [daily average, minimum -maximum values]
- Respiration rate (breath per minute) [daily average, minimum -maximum values] (derived parameter)
- Ratio of inspiration vs expiration time [daily average min-max] (derived parameter)
- Cough frequency (derived parameter)
- Sleep pattern (derived parameter)

Self-measured Variables:

- Self-reported COPD symptoms via the CAT questionnaire
- Self-reported activities (coughing, coughing with sputum production, spray use, non scheduled spray use, eating, going to bed, waking up, walking, climbing stairs, and physical exercise) as collected by the participant app
- Self-reported satisfaction with the study, collected via end of study questionnaire

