9.5 Study Size

Sample size calculation is based on the second part of the primary objective, especially on predicting exacerbations of a severe or moderate type as outcome.

Assuming a desirable sensitivity and specificity of 0.85 for our algorithm and requiring that the lower 95% confidence limit should be at least 0.50 (with a probability of 0.95) for this exploratory approach, the number of observed exacerbation events needed is 18 ([Flahault 2005](#)).

Assuming that patients with COPD within our eligibility criteria (GOLD stage II-IV with a history of at least 2 moderate and/or severe exacerbations within any 12 month period within the last 3 years and at least 1 moderate or severe exacerbation within the last 12 months) show a frequency of 2 moderate or severe exacerbations per year, participants with COPD will have 0.5 events in 3 months (the in-study time). Further assuming that event occurrence over 3 months for every individual participant follows a Poisson distribution with parameter $\lambda = 0.5$, the number of events in the overall study population is also Poisson distributed and the corresponding parameter is the sum of individual parameters λ . Calculations show that a λ of 30 is needed to reach an upper cumulative distribution probability of 0.99 for observing at least 18 exacerbations. Therefore, 60 participants are needed to observe at least 18 exacerbation events within the 3-month observation period.

The events of interest in the context of the present study are COPD exacerbations (severe or moderate), exactly the onset of an exacerbation. For building the binary classifier predictive models we also require “no exacerbation” events. We will sample such events randomly from periods with no exacerbations, avoiding 2 weeks before and after an exacerbation.

Considering a drop-out rate of 10%, the estimated number is 67 participants with COPD that need to be included in this study.

This recruitment number is also in good agreement with published studies with regards to the ability to build predictive models for exacerbations. Studies with similar recruitment numbers ([Yañez 2012](#)) have been able to predict exacerbations based on single parameters studied. Strong features can compensate for low numbers in COPD machine learning model building as shown in

[Al Rajeh 2020](#), and using several features improves the accuracy of predictive models as seen in [Jensen 2012](#).

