#### 2.1.4 Sensor measurements by Vivalink wearable device and ePRO diary

Unless indicated otherwise, the following variables are measured continuously throughout the observation period.

- Physical activity including stair climbing, (calculated based on continuous accelerometer measurement) [daily average] (derived parameter)

- Heart rate as beats per minute [daily average]
- Resting heart rate (resting state as determined by accelerometer, beats per minute) [daily average] (derived parameter)
- Heart rate variability reflecting differences in time intervals between 2 R-waves in the ECG (milliseconds) [daily average] of the following parameters:
  - SDRR (standard deviation of RR intervals),
  - SDNN (standard deviation of NN intervals),
  - SDNNI (Mean of the standard deviations of all the NN intervals for each 5 min segment of a 24 h HRV recording),
  - RMSSD (Root Mean Sum of Squared Distance),
  - ln(RMSSD) (natural logarithm of RMSSD),
  - pNN50 (percentage of successive RR intervals that differ by more than 50 ms)
  - SI (stress index),
  - LF power (low frequency fraction of HRV, 0.04 – 0.15 Hz),
  - HF power (high frequency portion of HRV, 0.15 – 0.40 Hz),
  - LF/HF (ratio of LF-to-HF power) (derived parameter)
- Temperature [daily average, minimum and maximum values] (derived parameter)
- Respiration rate (breath per minute) [daily average, minimum and maximum values]
- Ratio of in- vs expiration time [daily average, minimum and maximum values] (derived parameter)
- Cough frequency (derived parameter, count per day)
- Sleep pattern (derived parameter, hours of sleep)
- Self-reported activities as collected by the participant app, logged as activity per time-stamp, allowing for several logs of the same activity per day:
  - coughing,
  - coughing with sputum production,
  - spray use,
  - non-scheduled spray use,
  - eating,
  - going to bed,
  - waking up,
  - walking,
  - climbing stairs,
  - and physical exercise

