#### 3.4.2 Considerations for potential confounders and effect modifiers

Not applicable. All available features will be considered in the predictive modelling.

For objective 4, smoking status, and other relevant baseline covariates will be forced into the models.

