### 3.4.5 Analysis of outcomes

#### 3.4.5.1 Primary Objective 1

Descriptive statistics will be reported in terms of mean (SD) or median (IQR) for continuous variables, as well as counts and frequency (%) for categorical variables of sensor collected data described in section 2.1.4, comprised of

- physical activity,
- heart rate,
- resting heart rate,
- heart rate variability (10 variables),
- temperature,
- respiration rate,
- ratio of in- vs. expiration time
- cough frequency,
- sleep pattern (hours of sleep),
- frequency of additional medication

measured for each patient

1. at baseline (Day 0),
2. in the period Day 8 to Day 14 (intra-individual period average),
3. from 14 days prior to an exacerbation onset, in a 7-day sliding time window, in a 3-days sliding time window, and a 1-day sliding time window,
4. at the onset of an exacerbation (first day of exacerbation period),
5. from the end of an exacerbation to 14 days after, in a 7-day sliding time window, in a 3-days sliding time window, and a 1-day sliding time window,
6. 14, 21, and 28 days after an exacerbation.

The analysis will be repeated for different exacerbation severities:

1. Exacerbations of any (moderate or severe) severity are counted
2. Only severe exacerbations are counted
3. Only moderate exacerbations are counted
4. Only mild exacerbations are counted

Results will be reported in one table per parameter, with descriptive statistics indexing rows and measurement times indexing columns.

For each continuous parameter, mean values will be plotted across all daily measurement time points during the 3-month observation period, together with 95% CIs based on the normal approximation (t-statistic).

### 3.4.5.2 Primary Objective 2

To predict moderate or severe COPD exacerbations by building a statistical model employing sensor-derived data and demographic and medical covariates.

To generate several features needed as input to the model a number of algorithms (e.g., self-learning algorithms) for obtaining derived parameters such as cough frequency, physical activities and sleep pattern will be developed first using the label dataset obtained via the app (see Section 3.4.3).

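### The SAP does not say whether or how each participant's own sensor baseline, defined in the protocol, enters the exacerbation prediction model, and the protocol's fallback baseline can fall after the event being predicted

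*SAP*

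**What the plan says.** Protocol 9.3 Variables: "Values measured from day 8 to 14 will be used as baseline data (e.g. for determining parameter changes during the observation period". The same sentence gives use as a model co-factor as a second example. It disqualifies Day 8 to 14 when that window lies within 2 weeks of an exacerbation. The baseline is then the next 7-day period at a distance of 4 weeks from an exacerbation.

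SAP 3.4.5.2 states the aim of Primary Objective 2 as "To predict moderate or severe COPD exacerbations by building a statistical model employing sensor-derived data and demographic and medical covariates" and refers to SAP 3.4.3 for derived features. SAP 2.1.4 defines the sensor variables mostly as daily values, for example "Heart rate as beats per minute [daily average"]. The table in 3.4.3 explains how each derived variable is built. It contains no own-baseline value, no change from baseline and no fallback rule.

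The SAP names Day 8 to 14 once, as a descriptive time point for Primary Objective 1 (3.4.5.1), where it is an average within each individual. SAP 3.4.2 adds that "All available features will be considered in the predictive modelling", and 3.4.5.2 says that feature extraction and selection algorithms will be used.

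The SAP was written to protocol version 2.0. The only change logged for version 3.0 is the number of centres, so a version lag does not explain the gap.

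**The concern.** Heart rate, heart rate variability, activity and respiration rate can be expected to differ between people, whereas the event to be predicted is an onset within a patient (Protocol 7). A classifier given only levels must find a departure from a person's usual state against the spread between persons. Protocol 9.3 supplies the reference needed to remove that spread, and the SAP does not say whether the primary model uses it.

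The silence carries risk in two directions. Leaving the baseline out can understate what the sensors can do. Adding it later by following the protocol's fallback literally can overstate it, because the reference period for an early event may lie in that event's recovery phase. About 30 events are expected (60 participants at 0.5 each). Settling the matter after seeing the data would add analytic freedom to the sensitivity, specificity and AUC that are the primary result.

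**Working it through.** **1. The plan's own figures.** Protocol 9.5 starts from "Assuming a desirable sensitivity and specificity of 0.85 for our algorithm", "requiring that the lower 95% confidence limit should be at least 0.50 (with a probability of 0.95"), and concludes that "the number of observed exacerbation events needed is 18". With a one-sided exact 95% limit, 13 of 18 detected gives a lower limit of 0.502, and P(X ≥ 13 | n = 18, p = 0.85) = 0.958. So 18 is reproduced. The protocol then takes it that "participants with COPD will have 0.5 events in 3 months (the in-study time"), so 60 × 0.5 = 30 expected events. P(Poisson(30) ≥ 18) = 0.993, and 60/0.9 = 66.7, rounded up to 67. Nothing below changes 18, 60 or 67.

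**2. Where the baseline appears.**

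| Place | Day 8–14 baseline | Change from it | Fallback rule |
|---|---|---|---|
| Protocol 9.3 | yes | yes, as an example use | yes |
| SAP 3.4.5.1 (Objective 1) | yes, descriptive | no | no |
| SAP 3.4.3 (derived variables) | no | no | no |
| SAP 3.4.5.2 (Objective 2) | no | no | no |
| SAP 3.4.5.4 (Objective 4) | no | change in sensor variables named, reference not stated | no |

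For Objective 4 the SAP names change in the sensor variables and possible patient-level random effects. Objective 2 has no counterpart.

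**3. Timing of the fallback.** Day 14 plus 2 weeks is Day 28, so an onset on or before Day 28 puts the Day 8–14 window within the 2-week distance. At a constant rate over 91 days that is 28/91 = 0.308. A 7-day period that starts after Day 14 ends on Day 21 at the earliest. To lie 4 weeks before an onset, it would need that onset on Day 49 or later (21 + 28). So if the next period is read as the next later one, then for an onset by Day 28 it can only follow that event. For an onset on Day 20, for example, it starts no earlier than Day 48. Used as an input for predicting that onset, it is future data.

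**4. Size of the masking effect, as an illustration.** The documents give no between-person or within-person SD. Assumptions: one score on one day, total SD 1, and equal correlation rho between days of one person (rho is the between-person share of variance). The score reaches 0.85 sensitivity at 0.85 specificity once adjusted for a 7-day own-baseline mean.

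- Adjusted separation in residual SDs: 2 × z(0.85) = 2 × 1.0364 = 2.073.
- Residual SD given the baseline mean: s = √(1 − rho²/(rho + (1 − rho)/7)).
- Unadjusted sensitivity at specificity 0.85: Φ(2.073 × s − 1.036).
- Unadjusted AUC: Φ(2.073 × s/√2), against 0.929 adjusted.

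| rho (assumed) | s | Sensitivity | AUC | P(at least 13 of 18) |
|---|---|---|---|---|
| adjusted | – | 0.850 | 0.929 | 0.958 |
| 0.1 | 0.978 | 0.839 | 0.924 | 0.944 |
| 0.2 | 0.934 | 0.816 | 0.915 | 0.903 |
| 0.3 | 0.880 | 0.785 | 0.902 | 0.827 |
| 0.5 | 0.750 | 0.698 | 0.864 | 0.526 |
| 0.7 | 0.583 | 0.569 | 0.804 | 0.140 |

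**5. Change alone, or change plus baseline value.** If the feature is the change score by itself, the raw level reaches √((1 − rho)(1 + 1/7)) times the change score's separation. This ratio is 1 at rho = 0.125, and below that the raw level does as well or better. Offering the baseline value together with the change avoids this loss in the illustration, at the price of more inputs.

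**The case against.** The strongest reply is that the SAP is silent and does not exclude the baseline. SAP 3.4.5.2 has no closed feature list and no input window. The statements on available features and on feature extraction leave room for baseline or change features, and the Day 8–14 average is already computed for Objective 1. Protocol 9.3 offers its uses as examples and does not name the exacerbation model. All of this stands. A reader might infer that the SAP rules the baseline out of Objective 2, and the documents do not support that. They do leave the choice, the reference period and the handling of early events open for a primary analysis.

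A reader might also infer that every sensor feature is weakened. That goes too far. SAP 3.4.3 already treats temperature as a relative value, although it ties it to initial calibration values and not to Day 8–14.

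The loss is also easily overstated. It would be tempting to say that the chance of 13 of 18 falls by at least 13 points, but that floor exists only if rho is at least 0.3. At rho 0.1 the fall is about 1 point and at 0.2 about 6. If the inputs cover several days, earlier unshifted days carry much of the same information as the baseline; under the assumed correlation, seven such days carry as much. Lung function, GOLD stage, age and BMI may absorb more of the spread.

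Finally, the study is exploratory and its models are to be validated later (Protocol 7 and 9.9). That lowers the stakes but does not remove the need to say what the primary model is built from.

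**Conclusion.** The point holds as a gap in specification. Protocol 9.3 defines an own sensor baseline and mentions model building as a use; SAP 3.4.3 and 3.4.5.2 do not say whether or how it enters Objective 2. Two consequences follow, and each is conditional.

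- **Levels only:** between-person spread can mask the signal. The sensitivity of 0.839 to 0.569 for rho 0.1 to 0.7, against 0.85, is an illustration for a single score on a single day. It is not an estimate for this study.
- **Protocol fallback used as a predictor:** for onsets up to about Day 28 the baseline can post-date the event. The 31% assumes a constant onset rate over 91 days. Counting only onsets before the Day 8–14 window is complete would understate the affected share, because the 2-week rule reaches to Day 28.

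The documents do not support a claim that the trial will miss a true sensor signal, or that the planned 18 events are too few for this reason.

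**What to change.** In SAP 3.4.3 and 3.4.5.2:

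- Pre-specify, for each sensor variable, the change from the participant's own baseline, with the baseline value as co-factor, as candidate inputs to Objective 2.
- Compute both only from exacerbation-free days before the prediction day, with the same rule for event days and sampled non-event days.
- Do all feature selection inside the cross-validation.
- Report performance with and without these features.
- Reconcile this with the fallback in Protocol 9.3, so that no post-event period serves as baseline for predicting that event.

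The data are already being collected, so the cost is SAP text, derived variables and a clarification of the protocol's baseline rule. There are two downsides. With the SAP's own count of 17 sensor variables (3.4.5.3), a baseline and a change for each makes 2 × 17 = 34 candidate inputs against about 30 expected events, so selection or penalisation is needed. Early onsets will also have a short or missing baseline; they should be flagged and their number reported.

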Specifically, this study aims at predicting 2 target outcomes: acute exacerbations of COPD (AECOPDs) as defined by the GOLD initiative, and the CAT score as a proxy for patients' disease status. The start of an exacerbation within a patient, regardless of how many exacerbations the patient may have experienced before, will be predicted based on sensor data preceding the

exacerbation, and using basic covariates as well. For type of exacerbations, the severe and moderate exacerbations are considered as our main target as these are linked to the need of urgent medical intervention and will predict those as a group, but also separately (distinguish by type), if possible. Mild exacerbations, the relevance of which is currently a subject of investigation in the field, will also be explored.

For the CAT score, the aim is to predict the total score (max = 40) from the sensor data, and changes in the CAT score of ≥ 2 based on the MCID. With this approach, it is aimed to use the model built on sensor data as an objective means to reflect patients' disease status. While for the prediction of exacerbations the aim is to predict them as early as possible, i.e. days before an exacerbation, for the CAT/disease status prediction the aim is to reflect the daily status.

CCI

This study is exploratory in nature and any predictive models will need to be validated in future studies. A future remote patient monitoring (RPM) solution for patients with COPD built on these models will have 2 prime utilities: First, ameliorating or preventing exacerbations and their negative sequelae by early treatment intervention and second, to provide physicians and patients with a highly granular and precise view on the current disease status and past changes. Such information can be used by the treating physician to optimize therapeutic regimens and by the patients to accompany and optimize lifestyle changes. By using a multimodal sensor approach we intend to increase the accuracy of our predictive models beyond what has been described in the literature and thereby increase their clinical utility.

8 Research Question and Objectives

The aim of the study is to investigate the correlation of real-world sensor-derived biometric data obtained via a wearable device with clinical parameters and PROs for monitoring disease activity and predicting exacerbations for patients with COPD.

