9.7.2.1 Primary Objectives

Primary objective 1): To describe the distribution of sensor collected data on physical activity, heart rate, heart rate variability, temperature, respiration rate, cough frequency, and sleep pattern, by severity of COPD exacerbations.

This analysis will be performed on the COPD participants set.

- Sensor collected data on physical activity, heart rate, heart rate variability, temperature, respiration rate, cough frequency, sleep pattern, at baseline (Day 0), in the period Day 8 to Day 14, and shortly prior (14 days prior to, 7 days prior) to, during an exacerbation and after an exacerbation (8 to 14 days after, 2 weeks after, 3 weeks after, up to 4 weeks after an exacerbation) will be reported as mean (SD) and/or median (Interquartile Range) for continuous variables and counts and frequency (%) for categorical variables. The analysis will be done on the group of severe or moderate exacerbations and on exacerbations by type.

Primary objective 2): To predict moderate or severe COPD exacerbations by building a statistical model employing sensor-derived data and demographic and medical covariates.

This objective aims at predicting the occurrence of a severe or moderate exacerbation, in other words, predicting an event out of the combined group of severe and moderate exacerbations. It is desirable to predict an AECOPD as early as possible, therefore dependency of model metrics on the time period before exacerbation will be explored.

As input to the model a number of algorithms (e.g. self-learning algorithms) for obtaining derived parameters such as cough frequency, physical activities and sleep pattern, heart rate variability, temperature, respiration pattern, cough frequency, or sleep pattern will be developed first using the labeling of activities dataset obtained via the app. Said derived features will help to understand the importance of different raw data patterns, so that explanatory models can be built on top of the machine learning algorithms (Molnar 2022), as a way to support rationalization for physicians and regulatory organizations.

Different machine learning algorithms (e.g. gradient boosting, SVMs, K-nn) will be evaluated, and their performance will be assessed by estimating their accuracy, specificity, sensitivity, and area under ROC metrics.

This analysis will be performed on the COPD participants set.

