## 2.3 OUTCOME DEFINITIONS

### 2.3.1 Outcomes for primary objectives

The primary outcomes are based on COPD exacerbations. Exacerbations are classified as

- 1) mild if they are treated with short-acting bronchodilators only,
- 2) moderate if they are treated additionally with antibiotics or oral corticosteroids, or
- 3) severe if the patient visits the emergency room or requires hospitalization because of an exacerbation.

The occurrence of exacerbations during the observation period is measured as follows.:

- For moderate/severe exacerbation requiring a physician's intervention, exacerbation details will be recorded via eCRF by the clinical site. Severity, onset and duration will be derived according to the definition above from the documented COPD medication associated with the patients' exacerbation visit. The definition details for COPD medication and ATC codes will be finalized during the planned Data review meeting prior to the final analysis.
- For mild exacerbations: self-reported; treated by the participant without intervention by a physician will be documented in the patient application labeling section (days with added treatment: short-acting bronchodilators only). The start date and end date of addition of short-acting bronchodilators can thus be retrieved from the patient application. The documented use of additional medication (Bedarfsmedikament) will be considered as a mild exacerbation with the following rules for start and end days:
  - A mild exacerbation must start with at least 2 consecutive days of additional medication reported, the first day of consecutive medication will determine the start of the exacerbation.
  - If there are gaps in the additional medication reporting, a maximum of 2 days is allowed to be considered only one exacerbation. A minimum of 70% of the days must have additional medication reported. The end date of the exacerbation is the last day where both these rules are fulfilled.
- Any exacerbations that happen within 5 days will be considered as overlapping, as well as exacerbations that have an intersection in their start and end dates. Overlapping exacerbations will be considered as only one and classified as the graver one. (4)
  - If all overlapping exacerbations have the same type, the start date is the start date of the first exacerbation, and the end date of the last one.

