- If the overlapping exacerbations have different types, the start date will be the start date of the first moderate or severe exacerbation, and the end date is the end date of the last moderate or severe exacerbation.

The following exacerbation-related outcomes are required for the analysis of primary objectives:

1. Time points (start and end dates) of mild/moderate/severe exacerbations for descriptive analysis of sensor variables (see Section 2.1.4)
2. Occurrence of moderate/severe exacerbations as binary outcome measured at the onset date of an exacerbation for predictive analysis. An event is the occurrence of a moderate/severe exacerbation. Non-exacerbation events (for definition see Section 1.3.2) will be sampled randomly from time points (days) outside of exacerbation periods (defined by start and end dates of each exacerbation) and avoiding 2 weeks before the onset time (day) and two weeks after the end time (day) of an exacerbation.

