Different machine learning algorithms will be evaluated, and their performance will be assessed by estimating their accuracy, specificity, sensitivity, and area under ROC metrics. Other usual evaluation metrics such as precision, positive predictive value (PPV), negative predictive value (NPV), F1-score will be computed.

This analysis will be performed on the COPD cohort. Internal cross-validation will be tested.

The following models will be used:

- Logistic regression
- Random Forest
- K-nearest neighbors
- Boosting methods (e.g., Gradient boosting machine, GBM)
- Support vector machines (SVM)

Other methods may be tested.

The development of those models will be based on the machine learning algorithms implementation of scikit-learn (12), a python package designed for predictive data analysis. Other packages may be considered if needed (e.g., H2O (13)).

To optimize the performance of the models, feature extraction and selection algorithms will be used.

Explanatory models will be built on top of the selected machine learning algorithm (14), as a way to support rationalization for physicians and regulatory organizations. Depending on the selected ML model selected, either model specific (for logistic regression, decision trees, k-nearest neighbors) or model agnostic methods will be considered (global methods as PDP, ALE, functional decomposition, and local methods as LIME and Shapley values).

### 3.4.5.3 Secondary Objective 3

Objective 3 will be analyzed on the COPD cohort. For each pair of variables and outcomes ( $x, y$ ) defined below, Pearson's correlation coefficient will be computed together with a 95% asymptotic confidence interval based on Fisher's Z transform.

In case of low variability in parameter values (e.g., exacerbation count), parameters may be treated as ordinal and analyzed in terms of Kendall's Tau statistic with non-parametric confidence interval (see (15)).

The following variable groups and outcomes will be paired and assessed at the indicated time points:

Group x	Group y	Time points for assessment
Sensor data (see section 2.1.4), daily averages (17 variables): physical activity, heart rate, resting heart rate, heart rate variability, temperature, respiration rate, ratio of in- vs expiration time, cough frequency, sleep pattern (hours of sleep)	CAT summary score: Self-assessed patient's health status by CAT questionnaire.	Baseline (Day 0), End of study visit

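### SAP 3.4.5.2 sets no feature cut-off and no lead time for the exacerbation model, so its reported accuracy may include onset-day information and carry no stated warning time

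*SAP*

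**What the plan says.** **Protocol.** Section 7 sets the purpose of the exacerbation model: "the aim is to predict them as early as possible, i.e. days before an exacerbation". It also says that the start of an exacerbation "will be predicted based on sensor data preceding the" exacerbation. Section 9.7.2.1 turns the aim into an analysis under primary Objective 2: "dependency of model metrics on the time period before exacerbation will be explored". The Objective 2 covariates in 14.1.2 include lung function and laboratory values from the moderate/severe exacerbation visit.

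**SAP.** Section 3.4.5.2 governs the same objective: "Different machine learning algorithms will be evaluated, and their performance will be assessed by estimating their accuracy, specificity, sensitivity, and area under ROC metrics". It adds further metrics, five named methods, internal cross-validation, feature selection and explanatory models. It contains no horizon, feature window or performance by lead time. Section 2.3.1 defines the outcome: "Occurrence of moderate/severe exacerbations as binary outcome measured at the onset date of an exacerbation for predictive analysis". The same section says how onset is found: "Severity, onset and duration will be derived according to the definition above from the documented COPD medication associated with the patients' exacerbation visit". Control days are drawn at random, avoiding two weeks before and after any exacerbation. Section 3.4.2 lets every available feature into the predictive models.

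Windows before onset (7, 3 and 1 days) appear in SAP 3.4.5.1, for the descriptive Objective 1. The 14 days before an event also appear in the mixed model for CAT in 3.4.5.4.

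**The concern.** A model meant to give warning has to be judged on information available before the event, with the length of the warning stated. The protocol recognises both points, but the SAP section from which the analysis will be programmed has neither.

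An analyst who follows SAP 3.4.5.2 could let the feature window run up to and include the onset day, or use laboratory values taken at the exacerbation visit, without breaching anything in the SAP. Sensitivity and AUC would then partly measure recognition of an exacerbation already under way. The sample size rests on a desired sensitivity and specificity of 0.85 (Protocol 9.5, SAP 1.3.2), which is tied to no horizon either. A result near 0.85 could therefore be read as meeting the target whatever warning it gives.

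**Working it through.** **1. The sample size and its horizon.** Inputs from Protocol 9.5 and SAP 1.3.2: sensitivity 0.85, lower 95% limit at least 0.50 with probability 0.95, 0.5 events per participant in 3 months, 10% drop-out.
- Exact binomial, one-sided 5%: the smallest n is 18, with success at 13 or more of 18. P(X ≥ 13 | 0.50) = 0.048 and P(X ≥ 13 | 0.85) = 0.958. This matches the stated 18.
- Poisson with mean 30: P(X ≥ 18) = 0.993. This matches the stated 0.99.
- 30/0.5 = 60, and 60/0.9 = 66.7, rounded up to 67. Both match.

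The figures reproduce. None of the inputs is a lead time.

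**2. What the SAP text allows on the onset day.**
- The case label sits on the onset day (2.3.1). That dates the label and does not say where the features stop.
- Controls lie more than two weeks from any exacerbation (2.3.1). Days 1 to 14 before an onset are thus neither cases nor controls. They can enter only as features, and no feature window is defined.
- All available features are admitted (3.4.2), and exacerbation-visit values are listed covariates (Protocol 14.1.2). A control day has no exacerbation visit, so such values are informative by construction.
- The protocol's restriction to preceding data refers to sensor data. It does not cover visit laboratory or lung function values.

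**3. How much accuracy could depend on lead time.** The documents give no figure, so this is an illustration. Assume one normally distributed feature with equal variance in cases and controls, and a mean shift of d SD. Then AUC = Φ(d/√2). Assume d = 1.5 at onset and a linear rise over either 3 or 14 days, so that k days before onset d = 1.5 × (3 − k)/3 (not below 0) or 1.5 × (14 − k)/14.

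| Days before onset | 3-day rise: d, AUC | 14-day rise: d, AUC |
|---|---|---|
| 0 | 1.50, 0.86 | 1.50, 0.86 |
| 1 | 1.00, 0.76 | 1.39, 0.84 |
| 3 | 0, 0.50 | 1.18, 0.80 |
| 7 | 0, 0.50 | 0.75, 0.70 |

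The same onset-day AUC is compatible with no warning at three days and with a useful one. Only metrics by lead time would tell the two apart.

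**4. Events lost by requiring prior sensor days.** Assume 60 completers, 91 days and a constant rate. Requiring L complete sensor days before onset leaves 30 × (91 − L)/91 expected events.

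| L | Expected events | P(at least 18) |
|---|---|---|
| 1 | 29.7 | 0.99 |
| 3 | 29.0 | 0.99 |
| 7 | 27.7 | 0.98 |
| 14 | 25.4 | 0.95 |

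L counts all prior days needed. A 7-day window ending 7 days before onset would therefore use about 14. If the window must also come after the Day 8 to 14 baseline, L = 7 leaves 30 × (91 − 14 − 7)/91 = 23.1 events, with P(at least 18) = 0.88.

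**The case against.** The strongest reply is that the protocol already answers the point. Section 7 limits sensor predictors to data preceding the exacerbation, so a classifier using onset-day sensor data would depart from the protocol. The commitment in 9.7.2.1 still stands: nothing says that silence in the SAP cancels it, and the SAP states that it reflects the protocol. This stands, and it rules out the reading that the lead-time analysis has been withdrawn. What remains is that the SAP does not turn the rule into a feature window, and that the rule does not reach exacerbation-visit values.

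A reader might also infer that the trial could not say whether exacerbations are predictable days ahead. The documents do not support that. Sensor data are collected continuously, Objective 1 describes them over the 14 days before onset, and Objective 4 models daily values in that period. Neither evaluates a classifier, but the data for doing so will exist. Nor does the SAP reduce the result to one set of figures, since several methods and metrics are reported.

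That the participant has usually reached care by the onset day is likewise an inference. The SAP derives onset from documented medication, with details left to a data review meeting, while Protocol 9.1.2.1 has the date of the exacerbation recorded in the eCRF.

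Finally, the study is exploratory, the protocol promises only to explore, and it fixes no horizons. Redacted SAP sections after Objective 5 and the content of the TLF plan cannot be checked. The Objective 2 section itself is visible, however, and the protocol's amendment log does not explain the gap.

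**Conclusion.** The point holds as a gap in specification. SAP 3.4.5.2 does not carry over the restriction to preceding sensor data or the exploration of metrics by time before the exacerbation. With an onset derived from visit-linked medication, unrestricted features and visit values among the covariates, the reported accuracy may include onset-day information and has no stated warning time.

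The size of the effect cannot be derived from the documents. A reader might conclude from the 3-day scenario that accuracy falls to chance three days ahead. That fall is built into the assumed shape, and the 14-day rise gives about 0.80 at the same lead. The range of 0.50 to 0.80 rests on an assumed 1.5 SD shift at onset in a single normal feature. No figure in the sample size section is wrong.

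**What to change.** Add three statements to SAP 3.4.5.2:
1. All time-varying features for a case or control day come only from days before that day. The day itself and any exacerbation-visit values are excluded.
2. Sensitivity, specificity and AUC are reported by prespecified lead time, for example 1, 3 and 7 days, matching the window lengths of Objective 1. The documents do not dictate these values, and others would serve if fixed in advance.
3. The lead time of the headline figure is named before the models are built, so that the best one is not chosen afterwards.

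The cost is SAP wording and extra model runs on data already collected. Reported accuracy may be lower than with onset-day data, and a few early events without enough prior sensor days drop out. The SAP should state how many prior days each lead time needs, so that this loss is visible.
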